All clinicians and clinic staff who will be involved in application of the headset to participants have had training from Rescape or PI on how to use to the system. The training video is available to all staff if they feel they need to renew their training. The training log has been recorded and will be added to the standard operating procedure file. (SOP).

Criteria for discontinuing or modifying allocated interventions

Participants are free to remove the VR headset at any point in the intervention. They will be informed of this prior to its application. Participants will be free withdraw consent and leave the trial at any point during the process. They do not have to give prior warning or any explanation. This will not change the clinical procedure being conducted. If participant becomes upset or display signs of anxiety during the procedure the distress protocol will be followed (Appendix 3)

There is a risk of cybersickness during the application of the headset. Patients will be informed of this during the consent process and informed to remove the headset should this occur. This is included in the distress protocol and the deviation log (Appendix 7).

Strategies to improve adherence to interventions

Potential participants will be shown photographs of the VR headset prior to enrolment in the trial via the PIL provided to ensure understanding of its involvement. If they are in the VR intervention arm, they will be given the opportunity to see the VR device prior to beginning the therapy. They will be given the opportunity to try the headset on prior to beginning the colposcopy consultation to ensure they are amenable to having it placed prior to the procedure.

Relevant concomitant care permitted or prohibited during the trial

Some patients attending colposcopy will only have an inspection performed of the cervix, other patients will have a biopsy or a LLETZ procedure performed. If a biopsy or LLETZ procedure is performed, the entire colposcopy experience will take longer and may be more painful than if only inspection is performed. If a patient needs a biopsy or LLETZ performed, this will not be known until the colposcopy inspection

has taken place, so it is not possible to stratify the study group arms prior to enrolment in the trial.

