Participants will complete a questionnaire (Appendix 6a) with STAI questions prior to randomisation to get a baseline anxiety level. This will be compared to the post procedural questionnaire (Appendix 6b) with the same questions to compare the actual anxiety levels during the procedure. Comparison will be made between the two arms.

Secondary Outcome

Pain reduction: Pain scores will be measured by a Numeric Rating Scale (NRS) from 0 through to 10. 0 represents “no pain” and 10 represents “worst pain imaginable”. This will be shown alongside a visual analogue scale (VAS) of pain on animated faces. This is a validated measure for pain, is easy to use, has high compliance rates and detects meaningful change. (29,30,31) Participants will be asked to state the “maximum pain felt, if only for one moment,” and also state the “average pain experienced,” throughout the procedure. Respondents will select the single number that best represents their pain intensity. Results from participants in the intervention arm will be compared to participants in the control arm.

Understanding the acceptability and effectiveness of VR in variations of patient demographics: Participants will be asked to state the following demographics – age, ethnicity, parity, menopausal status, previous attendances to colposcopy and previous treatments in colposcopy. Acceptability will be monitored by participants ongoing consent of using the VR headset. If a patient removes the headset before the colposcopy assessment is completed, this will be noted in the post procedural questionnaire and be noted that the patient did not find it acceptable. The demographics of this patient cohort will be reviewed to see how VR effects different patient demographics.

Feasibility and acceptance of intervention from clinicians’ perspective: Following completion of the colposcopy assessment, the clinician will be asked to complete a short survey of their experience using VR. (Appendix 6c) These will be questions on a Likert scale from “strongly disagree” to “strongly agree”. Clinicians will be asked did they find it easy to use the VR in their clinic, did they find it beneficial to the consultation, did they find it easy to communicate with the patient during the consultation.

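### Every early headset removal is coded as non-acceptance without a reason, and refusals at the try-on have no stated place in the acceptability measure

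*Combined protocol and SAP*

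**What the plan says.** All references are to the combined protocol and SAP.

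- **Plans for assessment and collection of outcomes, Secondary Outcome.** The general statement is "Acceptability will be monitored by participants ongoing consent of using the VR headset". The working rule follows: "If a patient removes the headset before the colposcopy assessment is completed", then "this will be noted in the post procedural questionnaire and be noted that the patient did not find it acceptable". The group so defined has a further use: "The demographics of this patient cohort will be reviewed to see how VR effects different patient demographics".
- **Criteria for discontinuing or modifying allocated interventions.** "There is a risk of cybersickness during the application of the headset". The instruction is "Patients will be informed of this during the consent process and informed to remove the headset should this occur". The next sentence places cybersickness in the distress protocol and in the deviation log (Appendix 7).
- **Strategies to improve adherence to interventions.** For patients already allocated to VR: "They will be given the opportunity to try the headset on prior to beginning the colposcopy consultation to ensure they are amenable". Nothing is said about recording those who are not.
- **Intervention description.** Removal at will is to be recorded; a reason is not mentioned. The clinician's form asks about difficulties with equipment and communication.
- **Adverse event reporting text.** All adverse events are to be reported.
- **Statistical methods.** No analysis or denominator is given for acceptability.

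**The concern.** The rule turns a behaviour (taking the headset off) into a judgement (the patient did not accept it) without asking why. A patient who feels sick and does as she was told, one who is distressed, one whose equipment fails and one who simply dislikes the experience all receive the same code. In the other direction, a patient who declines at the try-on has given about as clear a sign of non-acceptance as the trial can observe, yet she never reaches the event that triggers the code.

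Acceptability is both a stated secondary objective and a stated secondary outcome, and early removal is the only patient-side event defined for it. The removers are also the group whose demographics are to be examined. If one age group removed the headset more often, a reader could not tell whether VR made those patients unwell or whether they disliked it. If refusals clustered in another group, the review would not show it.

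**Working it through.** **Denominator.** The Sample size section gives 64 per arm and 128 in total (alpha 0.05, power 0.80, d = 0.5), then 141 after 10% for dropout. Taking alpha as two-sided, which the plan does not state, the noncentral t gives power 0.7952 at 63 per arm and 0.8015 at 64, so 64 is reproduced. The total follows as 128 × 1.10 = 140.8, rounded up to 141. (Dividing by 0.90 instead gives 142.2, so 143; this makes no difference here.) Allocation is 1:1 (Implementation), so the VR arm holds 141 / 2 = 70.5, or about 70. One patient is 1 / 70 = 1.4 percentage points.

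**Applying the text case by case to a VR-allocated patient.**

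1. *Removes the headset for cybersickness.* The discontinuation section says the patient is "informed to remove the headset should this occur". The outcome section then codes her as not finding VR acceptable.
2. *Removes it for distress, equipment failure or dislike.* Same code. The clinician's form may show an equipment problem, but no section says it changes the code.
3. *Refuses at the try-on.* She does not wear the headset during colposcopy, so the removal trigger cannot be met. The screening log in the Recruitment section concerns people who decline the study or are unsuitable; it does not name refusals after allocation.
4. *Keeps it on while unwell.* She is not coded as non-accepting. Her symptoms can be recorded through the deviation log and adverse event reporting.

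**Direction of the error.** The plan gives no rates, so every count below is assumed, on 70 VR patients, only to show how the measure behaves.

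| Assumed counts | Plan's rule | Refusals plus removals not due to cybersickness | All-cause non-use |
|---|---|---|---|
| 7 removals (3 for cybersickness), 0 refusals | 7/70 = 10.0% | 4/70 = 5.7% | 7/70 = 10.0% |
| 7 removals (3 for cybersickness), 4 refusals | 7/70 = 10.0%, or 7/66 = 10.6% of those who started | (4 + 4)/70 = 11.4% | (7 + 4)/70 = 15.7% |
| 0 removals, 7 refusals | 0/70 = 0% | 7/70 = 10.0% | 7/70 = 10.0% |

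The exact 95% interval for 7/70 is 4.1% to 19.5%.

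In the first row the rule overstates non-acceptance if cybersickness is regarded as a separate matter. In the third it misses non-acceptance altogether. In the second the two errors nearly cancel against one definition (10.0% against 11.4%) but not against all-cause non-use (15.7%). There is no fixed direction. The second row also shows an open denominator: the plan does not say whether it is everyone allocated or everyone who started.

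**The case against.** Four counter-arguments deserve an answer.

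*Cybersickness is recorded elsewhere.* This stands. A reader might infer that patients who stay unwell under the headset go uncounted and that tolerability is misstated. The documents do not support that: cybersickness is placed in the distress protocol and the deviation log, and all adverse events are to be reported, whether or not the headset comes off. What remains is that tolerability is not a defined outcome and no section reviewed links those records to acceptability. The Confidentiality section describes questionnaire results going to the statisticians and does not mention the deviation log. The principal investigator's separate data log might allow linkage, but none is planned.

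*Ongoing consent already covers refusal at the try-on.* This is a fair reading of the general statement. However, the only event the plan defines is removal before the assessment ends, so site staff following the text have no instruction to count a refusal.

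*Any-cause removal is a legitimate measure.* It is. A patient who stops because she feels sick may reasonably be said not to have found VR acceptable, and taking such patients out of non-acceptance could flatter the device. For that reason the fix reports all-cause non-use by reason and does not redefine non-acceptance to leave out illness.

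*The forms may already ask for a reason.* The appendices, including the post-procedure questionnaire, the distress protocol and the deviation log, were not available, so the absence of a reason field cannot be asserted. Even if one exists, the outcome definition as written still assigns a single code.

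**Conclusion.** The point holds as a defect in the definition of a descriptive secondary outcome. Two sections need reconciling: one instructs removal in a stated circumstance, and the other treats every early removal as non-acceptance. Try-on refusals after allocation also need an explicit place. No view is taken on when a headset should come off.

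The acceptability rate and the demographic review of removers may be misstated in either direction. The amount cannot be computed from the documents beyond 1.4 points per patient, assuming about 70 in the VR arm. A reader might be tempted to take the patient-involvement result (87% of 15 willing, so 13% not) as a refusal rate. It came from people interviewed before the trial, whereas those facing the try-on have already consented and been allocated, so it is not a usable estimate.

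The primary STAI analysis and the sample size are not affected. The change is worth making because it is nearly free and because reasons for removal cannot be reliably recovered afterwards.

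**What to change.** Before data collection starts:

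1. For every patient allocated to VR, record one usage status: refused at try-on, worn throughout, or removed early.
2. For refusal or early removal, add one coded reason: cybersickness, distress, dislike, equipment, communication, or other.
3. Reword the outcome. Report all-cause non-use (refusals plus early removals) over all VR-allocated patients, broken down by reason, in place of labelling every removal as non-acceptance. Base the demographic review on the same categories.
4. Report cybersickness separately among all who wore the headset, drawing on the deviation log and adverse event records, and state that these will be linked by study number. This covers patients who kept the headset on while unwell, whom a reason-for-removal field alone would miss.

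The cost is one extra line on a form, a rewritten outcome definition and a planned link to existing records. The reported acceptability rate may move up or down as a result.

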- Understanding the acceptability and effectiveness regarding anxiety reduction of VR interventions within the procedural groups and how these might vary as a function of different patient demographics.
- Feasibility and acceptance of intervention from clinicians' perspective
- To investigate if the introduction of VR have an impact on patients' attendance to follow up appointments

Study Design

Trial design

The “Mind over Cervix” trial is designed as a single centre, prospective, non-blinded, randomised control trial with two parallel groups to determine the superiority of VR headsets in patients’ anxiety reduction and pain reduction during outpatient colposcopy compared to standard care.

Study setting

The study will be carried out in the colposcopy outpatient clinic in Queen Elizabeth Hospital (QE), Gateshead, Gateshead Health Trust.

QE is a large tertiary referral centre for gynaecology and colposcopy in the north-east of England. Over 1700 patients attend the department for colposcopy annually. (24) Colposcopy is provided by consultant gynaecologists, consultant gynaecologists and nurse colposcopists.

Withdrawal Criteria

Patients can withdraw from the study at any time and without giving a reason. Deciding to withdraw or not take part in the study will not have any effect on the standard of care they receive. In addition, any staff member may withdraw their consent at any time without giving a reason.

Recruitment

Queen Elizabeth Hospital in Gateshead is a large tertiary referral centre for Gynaecology and colposcopy in the northeast of England. Over 1700 patients attend the department for colposcopy annually. (24)

Following prospective ethical and trust approval via IRAS, all patients who attend for outpatient colposcopy will be informed of the study prior to their arrival to the department. They will be sent a patient invitation leaflet (Appendix 1) to their home through the post 2-4 weeks prior to their appointment to inform them of the study and the fact they may be approached. On arrival to the department, a poster will be displayed in the department to remind attendees of the study and the potential for their participation (Appendix 1a). They will be given information again via the PIL (Appendix 1b) which will be provided by the clerical staff when they attend reception to check in for their appointment.

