Demographic characteristics will be explored for missing data and distribution abnormalities. Means and standard deviations will be used to characterise the sample. Analysis of covariance (ANCOVA) and non-parametric tests (Mann – Whitney) will be used to determine whether the VR intervention lead to a significant difference between baseline and follow up anxiety between control VR and control arm. Descriptive statistics (i.e. age, gender, ethnicity, previous attendance to colposcopy, menopausal status and parity) for the baseline values will be presented within each randomized controlled arm. P values will be used to estimate statistical significance for all analysis.

End of Study Definition

The end of study will be upon completion of the final visit of the last participant/volunteer enrolled in the trial.

Project Management Plan

PROJECT MANAGEMENT PLAN (with project milestones)			
Action	Timescale	Responsibility	Indicator / Outcome / Evidence
Develop protocol	Aug 23- Dec 23	Fellow and Supervisors	Creation of protocol to ensure robust methodology and outcome measures
Scoping exercise amongst service users	Oct 23- Dec 23	Fellow	Ensure in keeping with service users focus
Train staff on VR equipment	Oct 23 - ongoing	Fellow, Rescape	Train staff alongside Rescape to use equipment
Recruitment PPI work for patient information leaflets, questionnaires	Oct 23 - ongoing	Fellow, Research nurses	Approaching service users for feedback to ensure legibility
Begin recruitment of service users	March 24 – August 24	Fellow, Research nurses	Consenting and awareness
Begin trial and data collection	March 24 – August 24	Fellow, Research team, supervisors	Comparison of VR to standard care
Completion of data collection and writing up	Aug 24 – Dec 24	Fellow, Supervisors	Writing up analysis
Dissemination of information	Jan 25 – Aug 25	Fellow, supervisors	Conference presentations, publications

Oversight and monitoring

Composition of the coordinating centre

[name] (Principal investigator) *Clinical Research Fellow Gynaecological Oncology*

- Design and conduct of “Mind over Cervix”.
- Preparation of protocol and revisions
- Chair of steering group

- Overall responsibility for study milestones
- Preparation of case report forms (CRFs)
- Managing, monitoring and ensuring integrity of collaborative relationships

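### The only analysis stated for how VR's acceptability and anxiety effect vary with demographics is a review of headset removers; it names no comparison and includes no control patients

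*Combined protocol and SAP*

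**What the plan says.** The Secondary objectives list the acceptability of VR and its effectiveness in reducing anxiety, within the procedural groups, and "how these might vary as a function of different patient demographics". The trial summary table (key secondary outcomes) and the Outcomes section carry the same item.

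The method is under Plans for assessment and collection of outcomes, Secondary Outcome. Participants, without restriction to one arm, are asked for "age, ethnicity, parity, menopausal status, previous attendances to colposcopy and previous treatments in colposcopy". Then: "Acceptability will be monitored by participants ongoing consent of using the VR headset". Next: "If a patient removes the headset before the colposcopy assessment is completed, this will be noted in the post procedural questionnaire", and such a patient is counted as not having found VR acceptable. The paragraph ends: "The demographics of this patient cohort will be reviewed to see how VR effects different patient demographics".

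Statistical methods has two relevant elements. ANCOVA and Mann-Whitney tests "will be used to determine whether the VR intervention lead to a significant difference between baseline and follow up anxiety" between the arms. Descriptive statistics for age, gender, ethnicity, previous attendance, menopausal status and parity "for the baseline values will be presented within each randomized controlled arm". No subgroup analysis, interaction term or comparison of removers with non-removers appears there, and nothing is planned by procedure performed.

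**The concern.** The objective has two parts, and each needs a comparison. Variation in acceptability needs removal rates set against each other across patient groups. Variation in effectiveness needs the VR-versus-control difference in STAI set against itself across patient groups. The stated method supplies neither.

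A profile of removers can reflect the clinic's case mix: a feature common among removers may simply be common among all patients given the headset. Because the sentence says the review will show how VR affects different groups, such a profile could be reported as a demographic effect of VR. A real difference in anxiety benefit between groups would not be looked for at all.

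**Working it through.** **1. Who is in the cohort.** The sentence before the quoted one concerns patients who remove the headset, so the cohort is most naturally the removers. Under Intervention description, control patients have colposcopy without a headset and may try one only after their part in the study is complete. No control patient can therefore remove a headset during the procedure. The cohort contains no randomised contrast, whatever its size.

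**2. What a removers-only profile can say.** The documents give no removal rate. Assume 5% to 20% of about 70 VR patients (141/2 = 70.5): 0.05 × 70 = 3.5 to 0.20 × 70 = 14 removers. If 4 of 7 removers shared a feature, the exact (Clopper-Pearson) 95% interval for that share would be 18% to 90%.

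Now assume 9 removers among 70, of whom 6 are nulliparous. Removal by parity depends on the make-up of the whole VR arm:

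| Nulliparous in VR arm | Removal, nulliparous | Removal, others |
|---|---|---|
| 21 of 70 (30%) | 6/21 = 29% | 3/49 = 6% |
| 47 of 70 (67%) | 6/47 = 13% | 3/23 = 13% |
| 56 of 70 (80%) | 6/56 = 11% | 3/14 = 21% |

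The same nine removers fit higher, equal or lower removal among nulliparous patients. The profile can be read only beside the VR-arm totals. The planned baseline table would give those totals for five of the six characteristics; previous treatments is not in its list.

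**3. The plan's own sample size.** A two-sample t-test with d = 0.5, two-sided 0.05 and power 0.80 needs 63.77, so 64 per arm and 128 in total. Then 128 × 1.10 = 140.8, giving 141. The figure reproduces, but it is for the overall arm difference. Nothing is stated for this objective.

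**4. What an interaction analysis could deliver.** Take 64 analysed per arm, outcome SD = 1 and a share q of patients with the characteristic.

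SE = √[2/(64q) + 2/(64(1 − q))]; power = Φ(δ/SE − 1.96).

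- q = 0.5: SE = √(4/32) = 0.354 SD. The 95% CI half-width is 1.96 × 0.354 = 0.69 SD.
- δ = 0.5: Φ(1.414 − 1.96) = 29%. δ = 1.0: Φ(2.828 − 1.96) = 81%. The interaction detectable at 80% power is 0.99 SD.
- q = 0.2: power is 20% for δ = 0.5, and the detectable interaction is 1.24 SD.
- Baseline adjustment multiplies the SE by √(1 − ρ²). With assumed ρ = 0.5, SE = 0.354 × 0.866 = 0.306. Power is then 37% for δ = 0.5 and 90% for δ = 1.0. Over ρ = 0.3 to 0.7, power for δ = 0.5 runs from 32% to 51%.

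**5. Removal by characteristic.** With two groups of 35 in the VR arm, power to separate assumed removal rates of 20% and 5% is about 47%.

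**The case against.** The strongest reply is that the plan does not leave the removers in isolation. The by-arm baseline table describes the VR arm, and for categorical items the non-removers follow by subtraction. That stands: the acceptability half is under-described, and a reader who infers that no denominator exists anywhere in the plan goes too far.

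A reader might also infer that the trial cannot answer the objective, or that the demographic data go unused. Neither is supported. Demographics are asked of participants generally and STAI is collected before and after the procedure in both arms, so the limit lies in the stated analysis. The demographics are also used to characterise the sample and to describe the arms at baseline.

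The wording is loose, and the cohort could be taken to mean everyone given the headset. That reading would ease the acceptability problem. It still leaves out controls and names no comparison, so the effectiveness gap remains.

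Low power is a fair point too. A 0.5 SD interaction is as large as the whole effect the trial is sized for, and the better analysis would usually miss it. That is a reason to report estimates with intervals and call them exploratory. It does not support a method that carries no information on effect variation at any sample size.

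**Conclusion.** The concern holds for the analysis as written. The review of removers names no comparison with non-removers, although most of the VR-arm denominator would be available from the baseline table. With no control patients it cannot show whether the anxiety effect varies by demographic, and the overall arm comparison does not fill that gap. The part of the objective about procedural groups has no analysis either.

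This should be changed before the data are analysed, but it touches one secondary objective only; the primary comparison stands. The conclusion about the missing contrast rests on the text and needs no assumed figure. The sizes do rest on assumptions: removal of 5% to 20%, a 50:50 characteristic, 64 analysed per arm and a baseline correlation of 0.5. On those, an interaction of 0.5 SD would be detected about 29% of the time unadjusted and 37% adjusted.

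**What to change.** Replace the quoted sentence with two analyses and add a third.

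1. **Acceptability, VR arm only.** Report the proportion removing the headset by each of the six characteristics, removers against non-removers, with 95% CIs. Give the reason for removal only where it is already recorded. The protocol provides for recording removal and has a deviation log that covers cybersickness, but it does not say that a reason is always collected, and participants who withdraw need not give one.
2. **Effectiveness, all randomised patients.** Add arm-by-characteristic interaction terms, one characteristic at a time, to the ANCOVA of post-procedure STAI with baseline STAI as covariate. (Statistical methods does not name the covariate, so this should be stated.) Report estimates with CIs, labelled exploratory, for all six characteristics.
3. **Procedural groups.** Report the arm difference descriptively for inspection only, biopsy and LLETZ, noting that the procedure is known only after randomisation.

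The cost is a few lines of text. Items 1 and 2 use demographics, removal and STAI data already planned for collection. For item 3, confirm that the procedure performed is captured in the study data or can be linked from the clinical record, since the questionnaires are not in the text available. The downside is imprecision: the interaction intervals will be wide, and a null result will not show that VR works equally well in all groups.
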